10 SOFTWARE AND PROGRAMMING SPECIFICATIONS

All datasets, TLFs, and statistical analyses will be generated using SAS, Release 9.4 or higher (SAS Institute Inc., Cary, NC, USA). Computer-generated datasets, table, listing and figure output will adhere to the following specifications:

10.1 General Programming Specifications

- One SAS program can create several outputs or a separate SAS program can be created for each output at statistical programmer's discretion.
- Each output will be stored in a separate file.
- Dataset files will be delivered in SAS7BDAT format.
- TLF output files will be delivered in Word format / rtf format (or in pdf format if sponsor requests).

10.1.1 General

- All TLFs will be produced in landscape format, unless otherwise specified.
- All TLFs will be produced using the Courier New font, size 8, in sentence case.
- The data displays for all TLFs will have a 1.5-inch binding margin on top of a landscape oriented page and a minimum 1-inch margin on the other 3 sides.
- Headers and footers for figures will be in Courier New font, size 8, in sentence case.
- Legends will be used for all figures with more than 1 variable, group, or item displayed.
- TLFs will be in black and white (no color), unless otherwise specified.
- Specialized text styles, such as bolding, italics, borders, shading, and superscripted and subscripted text, will not be used in the TLFs, unless otherwise specified. On some occasions, superscripts 1, 2, or 3 may be used (see below).
- Only standard keyboard characters will be used in the TLFs. Special characters, such as non-printable control characters, printer-specific, or font-specific characters, will not be used. Hexadecimal-derived characters will be used, where possible, if they are appropriate to help display math symbols (e.g., μ). Certain subscripts and superscripts (e.g., cm², C_{max}) will be employed on a case-by-case basis.
- Mixed case will be used for all titles, footnotes, column headers, and programmer-supplied formats, as appropriate.

10.1.2 Headers

• All output should have the following header at the top left of each page:

Washington University School of Medicine

Protocol: PINIHL-WU

Data Cutoff Date: ddMonyyyy

- All output should have Page n of N at the top or bottom right corner of each page. TLFs should be internally paginated in relation to the total length (i.e., the page number should appear sequentially as page n of N, where N is the total number of pages in the table).
- The date (date output was generated) should appear along with program name and location as the last footer on each page.

10.1.3 Display Titles

Each TLF should be identified by the designation and a numeral. (i.e., Table 14.1.1). ICH E3 numbering is strongly recommended but sponsor preferences should be obtained prior to final determination. A decimal system (x.y and x.y.z) should be used to identify TLFs with related contents. The title is centered. The sample set should be identified on the line immediately following the title. The title and table designation are single spaced. A solid line spanning the margins will separate the display titles from the column headers. There will be 1 blank line between the last title and the solid line.

Table x.y.z
First Line of Title
Second Line of Title (if needed)
Sample Set

10.1.4 Column Headers

- Column headings should be displayed immediately below the solid line described above in initial upper-case characters.
- For numeric variables, include "unit" in column or row heading when appropriate.
- Sample set sizes will be presented for each treatment group in the column heading as (N=xx) (or in the row headings if applicable). This is distinct from the 'n' used for the descriptive statistics representing the number of subjects in the sample set.

10.1.5 Body of the Data Display

10.1.5.1 General Conventions

Data in columns of a table or listing should be formatted as follows:

- alphanumeric values are left-justified;
- whole numbers (e.g., counts) are right-justified; and
- numbers containing fractional portions are decimal aligned.

10.1.5.2 Table Conventions

- Units will be included where available.
- If the categories of a parameter are ordered, then all categories between the maximum and minimum category should be presented in the table, even if n=0 for all treatment groups in a

given category that is between the minimum and maximum level for that parameter. For example, the frequency distribution for symptom severity would appear as:

Severity Rating	N
severe	0
moderate	8
mild	3

Where relative frequencies are presented in these tables, zero relative frequencies will not be presented and so any counts of 0 will be presented as 0 and not as 0 (0%).

- If the categories are not ordered (e.g., Medical History, Reasons for Discontinuation from the Study, etc.), then only those categories for which there is at least 1 subject represented in 1 or more groups should be included.
- An Unknown or Missing category should be added to any parameter for which information is not available for 1 or more subjects.
- Unless otherwise specified, the estimated mean and median for a set of values should be printed out to 1 more significant digit than the original values, and standard deviations should be printed out to 2 more significant digits than the original values. The minimum and maximum (range) should report the same significant digits as the original values. For example, for systolic blood pressure:

N	XX	
Mean	XXX.X	
Std Dev	X.XX	
Median	XXX.X	
Range	XXX - XXX	

- P-values should be output in the format: "0.xxx", where xxx is the value rounded to 3 decimal places. Any p-value less than 0.001 will be presented as <0.001. If the p-value should be less than 0.0001 then present as <0.0001. If the p-value is returned as >0.999 then present as >0.999
- Relative frequency values should be printed to one decimal place, in parentheses with no spaces, one space after the count (e.g., 7 (12.8%), 13 (5.4%)). Values that round down to 0.0 will be displayed as '<0.1'. Unless otherwise noted, for all relative frequencies, the number of subjects in the sample set for the treatment group who have an observation will be the denominator. Relative frequency after zero counts should not be displayed and Relative frequency percentages equating to 100% should be presented as 100%.
- Unless otherwise specified, tabular displays of data for medical history, concomitant medications, and all tabular displays of adverse event data should be presented by the body system, drug class, or SOC by decreasing frequency, assuming all terms are coded. Within the body system, drug class and SOC, medical history (by preferred term), drugs (by ATC code), and adverse events (by preferred term) should be displayed in order of decreasing frequency. If incidence for more than 1 term is identical, they should then be sorted alphabetically. Missing descriptive statistics or p-values which cannot be estimated should be reported as "-".
- The relative frequency of subjects is normally calculated as a proportion of the number of subjects assessed in the relevant treatment group (or overall) for the sample set presented. However, careful consideration is required in many instances due to the complicated nature

- of selecting the denominator, usually the appropriate number of subjects exposed. Describe details of this in footnotes or programming notes.
- For categorical summaries (number and relative frequency of subjects) where a subject can be included in more than one category, describe in a footnote or programming note if the subject should be included in the summary statistics for all relevant categories or just 1 category and the criteria for selecting the criteria.
- Where a category with a subheading (such as system organ class) has to be split over more than one page, output the subheading followed by "(cont)" at the top of each subsequent page. The overall summary statistics for the subheading should only be output on the first relevant page.

10.1.5.3 Listing Conventions

- Listings will be sorted for presentation in order of treatment groups as above, subject number, visit/collection day, and visit/collection time.
- Missing data should be represented on subject listings as either a hyphen ("-") with a corresponding footnote ("- = unknown or not evaluated"), or as "N/A", with the footnote "N/A = not applicable", whichever is appropriate.
- Dates should be printed in SAS® DATE9.format ("DDMMMYYYY": 01JUL2000). Missing portions of dates should be represented on subject listings as dashes (--JUL2000). Dates that are missing because they are not applicable for the subject are output as "N/A", unless otherwise specified.
- All observed time values must be presented using a 24-hour clock HH:MM or HH:MM:SS format (e.g., 11:26 or 11:26:45). Time will only be reported if it was measured as part of the study.
- Units will be included where available.

10.1.6 Footnotes

- A solid line spanning the margins will separate the body of the data display from the footnotes.
- All footnotes will be left justified with single-line spacing immediately below the solid line underneath the data display.
- Footnotes should always begin with "Note:" if an informational footnote, or 1, 2, 3, etc. if a reference footnote. Each new footnote should start on a new line where possible.
- Footnotes will be present on the page where they are first referenced and thereafter on each page of the table, unless the footnote is specific only to certain pages. subject specific footnotes should be avoided.
- Footnotes will be used sparingly and must add value to the table, figure, or data listing. If more than six lines of footnotes are planned, then a cover page may be used to display

- footnotes, and only those essential to comprehension of the data will be repeated on each page.
- The last 2 lines of the footnote section will be a standard source that indicates the name of the program used to produce the data display, date and time the program was run, and the listing source (or data source for a listing) (i.e., 'Program: myprogram.sas Listing source: 16.x.y.z').

11 QUALITY CONTROL

11.1 Specifications

Once the SAP is finalized, dataset and TLF specifications will be developed and reviewed by the study team. An internal round table review of draft specifications will be conducted by the Lead Programmer, Lead Validator, Lead Statistician and Senior Reviewer (or member of Statistics Management).

The client will have the opportunity to review, comment and approve (via signature) all dataset and TLF specifications.

11.2 Outputs

Validation of analysis datasets and tables are conducted through independent parallel programming of the statistical output according to the agreed upon specifications defined in the protocol, SAP, table shells, and dataset specifications. In this process, two programmers working independently (i.e., without input from one another), program the same output and compare results (via SAS PROC COMPARE). Any discrepancies are discussed and resolved, and the validation cycle is repeated until no further differences are noted between the two outputs.

All programs are submitted in batch mode to document the results of the PROC COMPARE indicating no unequal observations. Additionally, tracking logs are maintained which document all QC and validation findings and their resolution.

For CDISC datasets the Pinnacle 21 report will be used to validate the datasets for CDISC compliance.

Once the validation cycle is complete, the output (dataset or TLF) is provided for the lead statistician's review as well as an internal round table review including the Lead Programmer, Lead Validator, Lead Statistician and Senior Reviewer (or member of Statistics Management).

For the delivery of the outputs for the Blinded Data Review Meeting (BDRM) the following team members from Pharm-Olam may join the output review round table as well: Medical Writer (if applicable), Data Manager (if applicable), Medical Monitor (if applicable) and Project Manager (if applicable).

The client will have the opportunity to review, comment and approve (via signature) all final datasets and TLFs as well.

12 APPENDICES

12.1 Index of Proposed Tables

Table Number	Table Title	Sample Set
Table 14.1.1	Subject Disposition	ITT Sample Set
Table 14.1.2	Protocol Deviation	Safety Sample Set
Table 14.1.3	Demographic and Baseline Characteristics	Safety Sample Set
Table 14.1.4	Medical and Surgical History	Safety Sample Set
Table 14.1.5	Concomitant Medications	Safety Sample Set
Table 14.1.6	Study Dose Administration	Safety Sample Set
Table 14.2.1.1	Primary Efficacy Analysis: Permanent Threshold Shift (PTS) in the Contralateral Ear Using Audiogram	ITT Sample Set
Table 14.2.1.2	Primary Efficacy Analysis: Permanent Threshold Shift (PTS) in the Contralateral Ear Using Audiogram	PP Sample Set
Table 14.2.1.3	Sensitivity Analysis 1: Permanent Threshold Shift (PTS) in the Contralateral Ear Using Audiogram	ITT Sample Set
Table 14.2.1.4	Sensitivity Analysis 1: Permanent Threshold Shift (PTS) in the Contralateral Ear Using Audiogram	PP Sample Set
Table 14.2.1.5	Sensitivity Analysis 2: Permanent Threshold Shift (PTS) in the Contralateral Ear Using Audiogram	ITT Sample Set
Table 14.2.1.6	Sensitivity Analysis 2: Permanent Threshold Shift (PTS) in the Contralateral Ear Using Audiogram	PP Sample Set
Table 14.2.1.7	Audiogram Results on Hearing Thresholds: Actual and Change from Baseline	ITT Sample Set
Table 14.2.1.8	Audiogram Results on Hearing Thresholds: Actual and Change from Baseline	PP Sample Set
Table 14.2.2.1	DPOAE OAE Amplitude: Actual and Change from Baseline	ITT Sample Set
Table 14.2.2.2	DPOAE OAE Amplitude: Actual and Change from Baseline	PP Sample Set
Table 14.2.2.3	DPOAE Noise Floor: Actual and Change from Baseline	ITT Sample Set
Table 14.2.2.4	DPOAE Noise Floor: Actual and Change from Baseline	PP Sample Set
Table 14.2.3.1	ECochG Results: Actual and Change from Baseline	ITT Sample Set
Table 14.2.3.2	ECochG Results: Actual and Change from Baseline	PP Sample Set
Table 14.2.4.1	WIN Test: Actual and Change from Baseline	ITT Sample Set
Table 14.2.4.2	WIN Test: Actual and Change from Baseline	PP Sample Set
Table 14.3.1.1	Overall Summary Adverse Events	Safety Sample Set
Table 14.3.1.2	Summary of Treatment-Emergent Adverse Events by System Organ Class and Preferred Term	Safety Sample Set

Table Number	Table Title	Sample Set
Table 14.3.1.3	Summary of Serious Treatment Emergent Adverse Events	Safatri Samula Sat
14.5.1.5		Safety Sample Set
	Summary of TEAEs by severity using the Common Terminology Criteria for Adverse Events (CTCAE	
Table 14.3.1.4	grades) by Maximum-reported Severity	Safety Sample Set
	Summary of Related Treatment Emergent Adverse	
Table 14.3.1.5	Events	Safety Sample Set
	Summary of TEAEs Leading to Study Drug	
Table 14.3.1.6	Interruption	Safety Sample Set
	Summary of TEAEs Leading to Study Drug	
Table 14.3.1.7	Withdrawn	Safety Sample Set
Table 14.3.2	Summary of Biochemistry Lab Results at Screening	Safety Sample Set
	Overall Summary of Physical Examination of Ears	
Table 14.3.3.1	Results at Screening	Safety Sample Set

12.2 Index of Proposed Listings

Listing Number	Listing Title	Sample Set
Listing 16.1.1	Subject Enrollment and Disposition All Subjects	All Subjects
Listing 16.1.2.1	Subject Inclusion and Exclusion Criteria	All Subjects
Listing 16.1.2.2	Protocol Deviations	All Subjects
Listing 16.1.3	Demographic Characteristics	All Subjects
Listing 16.1.4	Medical and Surgical History	Safety Sample Set
Listing 16.1.5	Hearing History and Occupation Exposure	Safety Sample Set
Listing 16.1.6	Concomitant Medications	Safety Sample Set
Listing 16.1.7	Study Drug Administration	Safety Sample Set
Listing 16.2.1	Audiogram Results on Hearing Thresholds	ITT Sample Set
Listing 16.2.2	Distortion Product Otoacoustic Emissions (DPOAE) Results	ITT Sample Set
Listing 16.2.3	Electrocochleography (ECochG) Results ITT Analysis Set	ITT Sample Set
Listing 16.2.4	Word in Noise (WIN) Test Results ITT Analysis Set	ITT Sample Set
Listing 16.2.5	LENS-Q Adapted for Surgical Noise Study Results at Screening ITT Analysis Set	ITT Sample Set
Listing 16.3.1.1	Serious Adverse Events	Safety Sample Set
Listing 16.3.1.2	Adverse Events Resulting in Death	Safety Sample Set
Listing 16.3.1.3	Treatment-emergent Adverse Events	Safety Sample Set
Listing 16.3.1.4	Treatment-emergent Adverse Events leading to Study Drug Interruption	Safety Sample Set
Listing 16.3.1.5	Treatment-emergent Adverse Events leading to Study Drug Withdrawn	Safety Sample Set

Listing Number	Listing Title	Sample Set
Listing 16.3.2.1	Clinical Laboratory Results at Screening: Biochemistry	Safety Sample Set
Listing 16.3.2.2	Pregnancy Test at Screening	Safety Sample Set
Listing 16.3.3	Physical Examination of Ears at Screening	Safety Sample Set

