## 1.2 NIHL and its Pathogenesis

After noise exposure, two phases of hearing loss can be measured. The first is a temporary threshold shift (TTS), which is greatest immediately after noise exposure, and gradually lessens within the first 24 hours. The second phase is a permanent threshold shift (PTS), which is measured two to three weeks after noise exposure (for recent review, Ryan et al., 2016; Liberman, 2016). These changes are typically monitored using behavioral pure-tone thresholds, distortion product otoacoustic emissions (DPOAE), or the auditory brainstem response (ABR) to generate an audiogram (a plot of threshold as a function of test frequency). The noise-induced damage is dependent on the noise pattern, intensity, and duration, with longer and louder noises being more hazardous than shorter or quieter sound exposures (Wang et al., 2002; Harding and Bohne, 2007; Chen et al., 2015). In addition, NIHL susceptibility differs markedly among individuals, resulting from the interaction of genetic and environmental factors (Clifford et al., 2016; Groth et al., 2016; Lavinsky et al., 2016). For example, in animals, the C57BL/6J mouse strain is more susceptible to noise than other mouse strains (Davis et al., 2001). In humans, individuals with specific single nucleotide polymorphisms (SNPs) in genes for certain antioxidant enzymes may be more susceptible to NIHL (Lin et al., 2009).

NIHL is caused by sensorineural damage, primarily to the sensory hair cells and primary auditory neurons of the cochlea (Liberman, 2017). Outer hair cells (OHCs) are particularly sensitive to noise. When OHCs are damaged, hearing thresholds increase due to a loss in amplification of the cochlear signal. Recently, Kujawa and Liberman (2006, 2009) have expanded on these classic findings with the observation that certain noise exposures at "benign" levels to rodents can result in

only TTS, but no PTS. Nevertheless, the animals show selective synaptic loss between inner hair cells (IHCs) and spiral ganglion neurons (SGNs) with high thresholds, ultimately accelerating hearing loss over time. Because this cochlear synaptopathy does not change the hearing threshold immediately, the term "hidden hearing loss" has been used to label the hidden synaptopathic injury, and this term has also been used to describe corresponding functional deficits that are assumed to be hidden behind the normal hearing threshold.

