#### 5.0 SCHEDULED ASSESSMENTS

## 5.1 Screening/Baseline/Preoperative Assessment

The screening and baseline assessments will occur within 30 days (+3 days) of surgery and include the following tests or procedures:

- 1. Documentation of demographic information, including gender, age, allergies, current medications, imaging related to surgery, and planned surgical approach.
- 2. Clinical examination of the ears.
- 3. Documentation of key clinical data such as confirmation of air conduction thresholds in the non-operated ears to be no worse than 25 dB HL for pure tone average 0.5, 1, and 2 kHz with no individual threshold greater than 30 dB HL, and no worse than 45 dB HL at 4 kHz and absence of ear disorder in the ear contralateral to surgery.
- 4. Collection of laboratory test results that include a pregnancy test\*, electrolyte panel, BUN, Cr, ALT, and AST.

  If these tests are not performed as part of pre-operative workup, we will obtain them for research purposes.
  - \*Women capable of becoming pregnant will be asked to have a pregnancy test before beginning this study. If a pregnancy test (urine or serum) is performed as part of pre-operative testing we will collect the results from the medical record for research purposes. Women capable of becoming pregnant will be instructed to use effective birth control methods and not to become pregnant while participating in this study as there may be unknown risks to the unborn child. There may be long-term effects of the treatment being studied that could increase the risk of harm to an unborn child. The study team must be notified if the birth control method fails while on the study and/or if the participant becomes pregnant while participating in this research study.
- 5. Blood sample will be collected for PGx surveys.
- 6. DPOAE, Audiogram, electrocochleography (ECochG), and WIN testing to document the measurements of the non-operated ear.

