## 5.5 Follow-Up Assessments

The follow-up assessments will occur after surgery and include the following tests or procedures:

- 1. DPOAE testing in recovery, within 8 hours after surgery.
- 2. Blood samples taken within 12 hours following the first pill for PGx surveys.
- 3. Collection of laboratory test results for research purposes that include an electrolyte panel, BUN, Cr, ALT, and AST. If these tests are not performed as part of clinical care post-operatively, we will obtain them for research purposes at the time of the PGx blood draw.
- 4. DPOAE, Audiogram, ECochG, and WIN testing 30 days (+/-3 days) after surgery.
- 5. Completion of the Hearing History and Occupation Exposure questionnaire 30 days (+/- 3 days) after surgery.
- 6. Documentation of adverse events.

Follow-up assessments will be planned at the stated time points; actual follow up times may vary due to patient logistics and compliance.

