#### 12.3 Sample Size Estimation

#### Sample size estimation for primary outcome measure.

The primary efficacy outcome will be the proportion of PTS positive subjects defined as the ratio of PTS-positive subjects to total number of subjects in each study arm/group. Using pilot data from a retrospective chart review of 75 similar patients undergoing ≥1-hour drill noise exposure, we estimate the proportion of PTS positive subjects in the placebo group will be 50%. We hypothesize that the expected effect of ZNS either pre-op or post-op will be a 50% reduction of the proportion of subjects with PTS positive as compared to placebo group. This is the desired clinically import effect for treating hearing loss for single dose of 100 mg ZNS.

The sample size for this study was calculated for the planned comparisons of each of the ZNS groups with the placebo group using a balanced design and a one-sided alpha level of 0.0125.

Based on the data from our retrospective study, using Fisher's exact test, we estimated that 78 subjects in the ZNS group and 78 subjects in the placebo group will be needed to provide us with 80.4 % power to detect a 50% reduction in the proportion of PTS positive subjects (from 50% to 25% corresponding to an

absolute proportion difference of 25%) at the 1-sided alpha level of 0.0125 for each ZNS-Placebo group comparison. Our one-sided hypothesis is supported by animal studies, and lack of any evidence of hearing loss as a side effect of ZNS in human studies. A total of 234 subjects will be enrolled to be randomized in this study. We will make all the needed effort to minimize and eliminate drop outs, and due to short term-follow-up of the study subjects in a period where they are under medical care, we do not expect any drop-outs or lost to follow-up.

All sample size calculations were carried out using PROC POWER procedure in SAS 9.4.

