## **Noise Exposure Group Assignment Based on Interview Questions**

- Participants with a response to 1.A., 2.A., or 4.A. of monthly or more frequent exposure are assigned to the higher noise group. Participants with less than monthly exposure are assigned to the lower noise group.
- Participants with a response to 1.C., 2.C, or 3.C. of 5 years or more are assigned to the Higher Noise group.

Version: 03 March 2023 Page 55 of 55

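### No noise-free period or recent-noise check precedes either audiogram, so a temporary shift can hide or create PTS and cost power

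*SAP*

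**What the plan says.** **Timing of the audiograms.** Protocol 5.1: "The screening and baseline assessments will occur within 30 days (+3 days) of surgery". Protocol 5.5 and the study calendar place the second audiogram at 30 days (±3) after surgery. Protocol 12.2.2 and SAP 5.2 also accept a rescheduled visit up to 30 days late. The audiometry paragraph in Protocol 5.1 describes the earphones, the button response and the frequency range. None of these places mentions quiet beforehand, a question about recent noise, or a repeat test to confirm a shift.

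**The hazard.** Protocol 1.2 says that a temporary shift peaks right after exposure and "gradually lessens within the first 24 hours".

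**Who is enrolled.** No exclusion criterion in Protocol 3.2 concerns recent noise. Appendix F: "Participants with a response to 1.A., 2.A., or 4.A. of monthly or more frequent exposure are assigned to the higher noise group". The most frequent answer to item 1A is daily occupational noise loud enough to require shouting.

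**The endpoint.** Protocol 4.0 and SAP 3.2 call a subject PTS-positive when one post-minus-baseline difference reaches 10 dB at any frequency from 2 to 6 kHz.

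**What is collected about later noise.** Protocol 5.5 lists "Completion of the Hearing History and Occupation Exposure questionnaire 30 days (+/- 3 days) after surgery", and the Visit 3 form (Appendix E, items 4 to 6) asks about loud noise since surgery. In the SAP the questionnaire appears only as Listing 16.1.5, "Hearing History and Occupation Exposure", which does not name a visit. No table, logistic or ANCOVA covariate, sensitivity analysis or stated per-protocol rule uses it.

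**The concern.** The trial measures a noise-induced threshold shift without controlling or recording noise just before the measurement.

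- If a participant comes to the baseline test soon after loud noise, the baseline threshold may be too high. Once it recovers, the day-30 difference is too small and a true PTS can be coded negative.
- If the noise comes shortly before the day-30 test, the difference is too large and an unharmed ear can be coded positive.

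A single difference at any one of several frequencies decides the outcome, and no confirmatory audiogram is planned, so nothing downstream would catch either error. Misclassification unrelated to arm shrinks the expected difference between ZNS and placebo. Planned power is only about 80%, so the design has little reserve for that.

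**Working it through.** **Inputs from the documents** (Protocol 12.3, SAP 2.7)
- Test level: "using a balanced design and a one-sided alpha level of 0.0125", Fisher's exact test.
- Size: "78 subjects in the ZNS group and 78 subjects in the placebo group will be needed to provide us with 80.4 % power".
- Rates: "we estimate the proportion of PTS positive subjects in the placebo group will be 50" (per cent), taken from a retrospective chart review of 75 patients and halved to 25% by ZNS.

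**Step 1: reproduce the plan's figure.** Enumerating the one-sided Fisher test over two independent binomials (78 per arm, 0.50 v 0.25, alpha 0.0125) gives 80.7%, close to the stated 80.4%. Also 3 × 78 = 234, as stated.

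**Step 2: model.** Let p be the true PTS rate, f the share of unharmed ears made positive by a temporary shift at day 30, and g the share of true PTS hidden by a temporary shift at baseline. Both are the same in every arm.

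Observed rate = p(1 − g) + (1 − p)f

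The observed difference is then 25 points × (1 − f − g) if 50% and 25% are true rates. The documents give no value for f or g, so every value below is an assumption.

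**Step 3: false positives at day 30 (g = 0), with 50% v 25% as true rates.**
- f = 2%: placebo 0.50 + 0.50 × 0.02 = 0.51; ZNS 0.25 + 0.75 × 0.02 = 0.265.
- f = 5%: placebo 0.50 + 0.50 × 0.05 = 0.525; ZNS 0.25 + 0.75 × 0.05 = 0.2875.

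**Step 4: the same, with 50% as the observed placebo rate.** Suppose the chart-review figure already contains such errors at the trial's own f and g. Then 0.50 = f + p(1 − f − g). ZNS halves p, so its observed rate is f + (0.50 − f)/2 = 0.25 + f/2, and g drops out.
- f = 2%: 0.50 v 0.26.
- f = 5%: 0.50 v 0.275.

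| False positives f | Power, 50% v 25% true | Power, 50% observed |
|---|---|---|
| 0 | 80.7% | 80.7% |
| 2% | 78.5% | 76.7% |
| 5% | 75.2% | 70.0% |

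**Step 5: masking at baseline (f = 0).**

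| Masked share g | Observed rates if 50% v 25% are true | Power | Power if 50% is observed |
|---|---|---|---|
| 5% | 47.5% v 23.75% | 76.5% | 80.7% |
| 10% | 45% v 22.5% | 72.2% | 80.7% |
| 20% | 40% v 20% | 63.1% | 80.7% |

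With f = g = 5% and true rates of 50% v 25%, the observed rates are 50% v 27.5% and power is 70.0%.

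**Step 6: type I error.** With no ZNS effect and equal error, both arms share one rate. For common rates from 50% to 57.5%, the exact one-sided error is 0.0100 to 0.0093, below 0.0125.

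**The case against.** **The frequency is unknown.** The documents give neither how often such shifts occur nor how large they are. To create PTS, recent noise must add enough at one frequency from 2 to 6 kHz to bring the difference to 10 dB. To hide it, the raised baseline must pull a true shift below 10 dB. This stands: the documents support only that temporary shifts can do these things. A reader might take the High Noise stratum as evidence of recent exposure. It is not, because monthly noise, or five years in an occupation, is enough to enter it, and no item concerns the days before testing.

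**The error is balanced.** Allocation is randomised, blinded and stratified on noise history, and that history is a covariate in the supportive model. This stands against any inference of bias towards ZNS or of a raised false-positive rate. It does not restore the lost power, because a history variable cannot correct a raised threshold on the test day. The LAeq8hr covariate does not help either: the only noise recording described is intra-operative (Protocol 5.4).

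**Masking may already be priced in.** The 50% comes from a chart review and may well be an observed rate. If so, the masking losses in Step 5 vanish. This stands. The false-positive loss remains, and is larger under that reading.

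**The Visit 3 answers could simply be analysed.** A reader might infer that excluding subjects who report noise since surgery would settle the matter. It would not. Items 4 to 6 cover the whole time since surgery without dates, count very brief exposures including music players, and say nothing about baseline. Exclusion would also select on a post-randomisation variable.

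**The questionnaire may have other uses.** The form carries coordinator and investigator review signatures, and Protocol 5.1 refers to a clinically approved audiometry procedure that is not reproduced and might contain pre-test instructions. So the supported statement is that no planned analysis uses the Visit 3 answers and neither document states a quiet period.

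**Conclusion.** The gap is real: neither document controls or records noise before the two audiograms that define the primary endpoint. The consequence is possible dilution and lost power, equal across arms in expectation, with type I error intact. Under assumed false-positive rates of 2% to 5% at day 30, power falls from 80.7% to between 78.5% and 75.2% if 50% v 25% are true rates, or to between 76.7% and 70.0% if 50% is the observed placebo rate. Masking at baseline adds to the loss only if 50% is a true, unmasked rate.

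A reader might go further and conclude that PTS from everyday noise will be wrongly credited to drilling. The estimand in SAP 3.1 is a difference between randomised arms, so attribution of cause is not what is tested. The case for change rests on its low cost, not on a demonstrated loss.

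**What to change.** 1. **Protocol 5.1 and 5.5.** Instruct participants to avoid shouting-level noise and gunfire for at least 24 hours before each audiogram. Record yes/no at both visits, and rebook within the existing visit windows if the condition is not met. The 24 hours is a minimum inferred from Protocol 1.2, which says that the shift lessens over that time, not that it resolves.
2. **SAP 7.1.1.** Add a supportive sensitivity analysis of the primary comparison that uses this new field, and leave the ITT analysis unchanged. Label it supportive, because the day-30 answer is given after randomisation. Do not exclude subjects on the undated Visit 3 items 4 to 6.

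Cost: one instruction, one field per audiogram, one extra table and an occasional rebooked visit.
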